8.1.7 Exploratory Efficacy Hypothesis

For cases which received the Triathlon TS Total Knee System with a Triathlon Tritanium Central Femoral Cone Augment, the exploratory hypothesis to be tested will be that the mean of KSS Objective Knee Score at 2 years postoperative is no worse than 86 with a non-inferiority margin of 5. The performance goal for 2-year KSS Objective Knee Score was calculated as 86 - 5 to give 81. That is, the following hypothesis will be tested:

H₀₁: u <=81 H_{A1}: u >81

Here, u is the mean KSS Objective Knee Score at 2 years postoperative.

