8.1.8 Exploratory Efficacy Analysis

For cases which received the Triathlon TS Total Knee System with a Triathlon Tritanium Central Femoral Cone Augment, A 95% two-sided confidence interval for the mean of KSS Objective Knee Score at 2 years will be computed. If the lower bound of the confidence interval is greater than 81, then it is supported that KSS Objective Knee Score at 2 years is no worse than 86 with a non-inferiority margin of 5. If the lower bound of the confidence interval is greater than 86, then it is supported that KSS Objective Knee Score at 2 years is better than 86.

The analysis for the additional data collection is in 8.4.1 Data Summary.

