8.4.2 Sample Size Justification

For primary efficacy objective, based on the literature review^{1,2}, it is reasonable to have a reference value of 97.2% for success rate at 2 years. A case success at 2 years is defined as no incidence of revision/removal of femoral or tibial cone augment for aseptic loosening within 2 years.

Based on Triathlon TS Outcome Study, it is reasonable to assume the expected success rate at 2 years is 98.8%, 100 cases will be needed to have a power of 80% to detect that the 2 year success rate is non-inferior to 97.2% with a margin of 2.5% at 5% significance level. After factoring a 30% lost to follow-up rate, a total of 145 cases will be needed.

For exploratory efficacy objective among cases receive the Triathlon TS Total Knee System with a Triathlon Tritanium Central Femoral Cone Augment, based on the existing data of this study for non-femoral central cone, it is reasonable to have a reference value of 86 for the mean of KSS Objective Knee Score at 2 years postoperative, with a standard deviation of 10, 32 cases will be needed to have a power of 80% to identify the mean of KSS Objective Knee Score at 2 years postoperative is Non-Inferior to 86 with a noninferiority margin of 5 at 2.5% significance level. After factoring a 30% attrition rate, a total of 46 cases will be needed.

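### The 32 evaluable (46 enrolled) central-cone cases for 80% power rest on a known-SD formula; with a t interval, the natural reading of section 8.1.8, power at 32 is about 78%, and 80% needs 34 (49 enrolled)

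*Combined protocol and SAP*

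**What the plan says.** Section 8.4.2 plans the exploratory objective on a reference mean of 86 for the 2-year KSS Objective Knee Score and an SD of 10. It says "32 cases will be needed to have a power of 80" per cent to show that the mean is "Non-Inferior to 86 with a noninferiority margin of 5 at 2.5% significance level". It continues: "After factoring a 30% attrition rate, a total of 46 cases will be needed".

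Section 8.1.7 turns the margin into a fixed threshold: "The performance goal for 2-year KSS Objective Knee Score was calculated as 86 - 5 to give 81". The null hypothesis is a mean of 81 or less.

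Section 8.1.8 gives the decision rule. "A 95% two-sided confidence interval for the mean of KSS Objective Knee Score at 2 years will be computed", and non-inferiority is supported if its lower bound exceeds 81. The section does not say how the interval is formed (t or normal quantile). The SD of 10 appears only in 8.4.2, as a planning value.

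Section 2.3 and the synopsis set the number of central femoral cone cases at 40 to 50.

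**The concern.** A sample size should be derived for the test that will be carried out. The figure of 32 is what results when the SD is treated as known. In the analysis, a confidence interval for the mean of about 32 scores would ordinarily take its SD from those scores and use a t quantile, which makes the interval a little wider. If so, 32 evaluable cases fall short of the stated 80%, even when the true mean, the SD and the attrition are exactly as assumed. The enrolled figure of 46 carries the same shortfall.

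At stake is the accuracy of one planning statement for an exploratory objective, and which number within the 40 to 50 range should be the working target.

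**Working it through.** **Inputs.** All are from section 8.4.2 unless noted.
- True mean 86, taken equal to the reference value (the power statement implies this).
- Threshold 81 (section 8.1.7), so the difference to detect is 86 − 81 = 5.
- SD 10.
- One-sided level 2.5%, matching the lower limit of the two-sided 95% interval in section 8.1.8.
- Power 80%.
- Attrition 30%.

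**Step 1: reproduce the plan's figures (SD known).**

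n = [SD × (z₀.₉₇₅ + z₀.₈₀) / difference]² = [10 × (1.960 + 0.842) / 5]² = 31.4, rounded up to 32.

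Power at 32 = Φ(0.5 × √32 − 1.960) = Φ(2.828 − 1.960) = Φ(0.868) = 80.7%.

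Enrolled: 32 / 0.70 = 45.7, rounded up to 46.

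Both stated figures reproduce exactly. A one-sided 5% level would give 24.7, so 25 cases; the plan therefore did use 2.5%.

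**Step 2: power when the SD is estimated (t interval).**

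The lower 95% limit exceeds 81 when the one-sample t statistic against 81 exceeds the 97.5% point of t with n − 1 degrees of freedom. If scores are normally distributed, that statistic follows a noncentral t with noncentrality (5/10) × √n.

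| Evaluable n | Power, SD known (z) | Power, SD estimated (t) | Enrolled at 30% attrition |
|---|---|---|---|
| 32 | 80.7% | 78.2% | 32/0.70 = 45.7, so 46 |
| 33 | 81.9% | 79.5% | 33/0.70 = 47.1, so 48 |
| 34 | 83.0% | 80.8% | 34/0.70 = 48.6, so 49 |

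The smallest n with at least 80% power is 34, and the matching enrolment is 49.

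**Step 3: would a normal-quantile interval rescue the figure?**

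If 8.1.8 were carried out with 1.96 and an SD estimated from 32 scores, the one-sided error would be P(t₃₁ > 1.96) = 2.95% and the two-sided coverage about 94.1%. Power at 32 would then be about 80.5%, but at a level above the stated 2.5%. At n = 32, the stated level and the stated power therefore hold together only if the SD is known.

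**Step 4: how sensitive is the gap?**

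With a t interval, 32 cases give exactly 80% power if the SD is 9.78 instead of 10. Across the permitted enrolment at 30% attrition, 40 × 0.70 = 28 evaluable cases give 72.3%, and 50 × 0.70 = 35 give 82.0%.

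**The case against.** The strongest reply is that nothing in 8.4.2 is miscalculated. A standard planning formula is applied correctly to its stated inputs, and both 32 and 46 follow. That stands. A reader might infer from the t-based figures that the plan contains an arithmetic error or contradicts itself. The documents support neither reading, because section 8.1.8 does not name a t interval; that has to be inferred.

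The second reply is that the gap is immaterial. It is under 2 power points, or 2 evaluable cases, and vanishes at an SD of about 9.8. The planning SD is a round 10, and the reference mean is drawn from cases in this study without the central cone, so the inputs are probably less certain than the difference between z and t. The noncentral t result also assumes normally distributed scores, which the plan does not state. This too stands, and it keeps the point minor.

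The third reply is that the enrolment rule of 40 to 50 already includes 49. That is correct, and it makes the correction cheap. It does not settle the matter, because the only target stated within the range is 46, which leaves about 32 evaluable cases (46 × 0.70 = 32.2). The lower power at 40 enrolled comes mainly from the width of the range and is a separate question.

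What the replies leave untouched is that the sentence presents 32 as the number needed for 80% without calling it an approximation, while the natural form of the planned interval does not reach 80% at 32.

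**Conclusion.** The point holds as a minor mismatch between the planning formula and the analysis. The figures of 32 and 46 are correct under the known-SD normal approximation and slightly optimistic for section 8.1.8. With a t interval, power at 32 is 78.2%, which is 1.8 points below the stated 80%. Reaching 80% needs 2 more evaluable cases (34) and 3 more enrolled (49, against 46).

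This rests on a true mean of exactly 86, an SD of 10, normally distributed scores, 30% attrition, and the inference that the interval uses an estimated SD with a t quantile.

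It would be wrong to conclude that the exploratory test itself is invalid. A t interval keeps its nominal level under those assumptions whichever formula was used for planning. The primary objective, with its 145 cases and its own decision rule, is unaffected.

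**What to change.** In section 8.4.2, do one of two things:
- keep 32 and 46, and state that 32 evaluable cases give about 78% power with a t interval (SD 10, true mean 86); or
- restate the requirement as 34 evaluable cases for 80% power, or 49 enrolled after 30% attrition.

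In section 8.1.8, state that the 95% interval for the mean is a t interval based on the sample SD.

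The cost is wording only. The first option lowers the stated power by about 2 points. The second moves the target by 3 cases, inside the 40 to 50 that section 2.3 already permits. The hypothesis, margin, threshold and endpoint stay as they are.

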	Triathlon TS Outcomes Study.
	Cases will be enrolled until at least 145 cases have received the
	Triathlon TS Total Knee System with a Triathlon Tritanium Cone
	Augment.
Number of Cases	
	Additionally, between 40-50 cases (within the study population) will
	receive the Triathlon TS Total Knee System with a Triathlon Tritanium
	Central Femoral Cone Augment.

	Triathlon TS Total Knee System with Triathlon Tritanium Cone			
	Augments			
	Required Components :			
	1. Triathlon TS Femoral Component			
	2. Triathlon TS or Triathlon PS Tibial Insert			
	3. Triathlon TS Universal Tibial Baseplate			
	4. Triathlon TS Tibial Cone Augment and/or Triathlon TS Femoral			
	Cone Augment (between 40-50 cases implanted with Triathlon			
	TS Central Femoral Cone Augment)			
Study Dovico	The femoral component and tibial baseplate must be used in a			
Study Device	cemented application. The cone augments must be used in a			
	cemented application with respect to the Triathlon TS Femoral and			
	Tibial Components, and a cementless application with respect to the			
	prepared bone.			
	The subject's patellar component may or may not be revised based			
	upon surgeon discretion. If revised, an X3 or N2Vac Triathlon Patellar			
	Component must be used in a cemented application.			
	Additionally, a variety of compatible Triathlon TS device accessories			
	may be used, as indicated in the surgical protocol.			

	Inclusi	ons:
	Α.	Patient has signed an IRB/EC approved, study specific
		Informed Patient Consent Form.
	В.	Patient is a male or non-pregnant female, skeletally mature and
		age 18 years or older at time of study device implantation.
	C.	Patient is a candidate for revision of all femoral and tibial
		components of a total knee replacement.
	D.	Patient is willing and able to comply with postoperative
		scheduled clinical and radiographic evaluations and
		rehabilitation.
	Exclus	ions:
Inclusion/Exclusion	E.	Patient has a Body Mass Index (BMI) > 45.
	F.	Patient has an active or suspected latent infection in or about
Criteria		the affected knee joint at time of study device implantation.
	G.	Patient has a neuromuscular or neurosensory deficiency, which
		limits the ability to evaluate the safety and efficacy of the
		device.
	Н.	Patient is diagnosed with a systemic disease (e.g. Lupus
		Erythematosus) or a metabolic disorder (e.g. Paget's disease)
		leading to progressive bone deterioration
	I.	Patient is immunologically suppressed or receiving steroids in

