2.3 Number of Subjects

Cases will be enrolled until at least 145 cases have received the Triathlon TS Total Knee System with a Triathlon Tritanium Cone Augment. Additionally, between 40 - 50 cases (within the study population) must receive the Triathlon TS Total Knee System with a Triathlon Tritanium Central Femoral Cone Augment.

3 Device Description

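### Section 8.4.2 asks for 46 central-cone cases for 80% power on the exploratory KSS test, but the enrolment rule is met at 40, where power at the planned 30% attrition is about 75%

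*Combined protocol and SAP*

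**What the plan says.** Section 8.4.2 (Sample Size Justification) sizes the exploratory objective for cases given the Central Femoral Cone Augment. It takes a reference mean of 86, a standard deviation of 10 and a "noninferiority margin of 5 at 2.5% significance level", and concludes that "32 cases will be needed to have a power of 80% to identify the mean of KSS Objective Knee Score" is non-inferior to the reference. It then allows for attrition: "After factoring a 30% attrition rate, a total of 46 cases will be needed".

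The enrolment requirement is stated in three other places, each time as a range:
- Section 2.3 (Number of Subjects): "between 40 - 50 cases (within the study population) must receive the Triathlon TS Total Knee System" with the central cone.
- Study Synopsis, Number of Cases row: "Additionally, between 40-50 cases (within the study population) will" receive it.
- Study Synopsis, Study Device row: "Cone Augment (between 40-50 cases implanted with Triathlon" central cones.

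None of the three gives 46 as a minimum. Section 8.1.8 (Exploratory Efficacy Analysis) sets the decision rule: "A 95% two-sided confidence interval for the mean of KSS Objective Knee Score at 2 years will be computed", and its lower bound is compared with 81. Section 8.3 imputes no missing data.

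**The concern.** A sponsor who stops central-cone enrolment at 40 complies with Section 2.3 and is 6 cases short of the number Section 8.4.2 calls for. Because nothing is imputed, a case without a 2-year score adds nothing to the 2-year mean, so attrition comes straight off the sample size.

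The primary objective is handled differently: the 145 derived in Section 8.4.2 reappears in Section 2.3 as a floor. The 46 does not.

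What is at stake is how a result would be read. The objective has a formal hypothesis, a confidence-interval rule and a stated power. If the lower bound missed 81 after only 40 cases had been enrolled, readers would judge that result against an 80% that did not apply.

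**Working it through.** **Inputs.** From Section 8.4.2: SD 10, margin 5, one-sided 2.5%, power 80%, attrition 30%. From Section 8.1.7: null mean 86 − 5 = 81. The one-sided 2.5% agrees with the lower bound of the 95% two-sided interval in Section 8.1.8. The true mean is taken as 86. The text calls 86 a reference value, but the plan's 32 follows only if it is also the assumed true mean. The effect is then 5/10 = 0.5 SD.

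**The plan's figures.**
- Evaluable: n = ((1.960 + 0.842) × 10/5)² = 31.4, rounded up to 32.
- Enrolled: 32/0.70 = 45.7, rounded up to 46.

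Both match, so the plan used the one-sample normal approximation and divided by the retained fraction.

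**Power across the permitted range.** Evaluable n is 0.70 × enrolled, rounded down.
- Normal approximation: power = Φ(0.5√n − 1.960). For n = 28 this is Φ(2.646 − 1.960) = Φ(0.686) = 75.4%.
- t interval: power from the noncentral t distribution with n − 1 degrees of freedom and noncentrality 0.5√n, one-sided 2.5%.

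| Enrolled | Evaluable at 30% attrition | Power, normal | Power, t |
|---|---|---|---|
| 40, 41 | 28 | 75.4% | 72.3% |
| 42 | 29 | 76.8% | 73.9% |
| 43, 44 | 30 | 78.2% | 75.4% |
| 45 | 31 | 79.5% | 76.8% |
| 46 | 32 | 80.7% | 78.2% |
| 50 | 35 | 84.1% | 82.0% |

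The normal-approximation shortfall from 80% is 4.6 points at 40 and 41 enrolled, 3.2 at 42, 1.8 at 43 and 44, and 0.5 at 45.

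If attrition is treated as random (each case retained with probability 70%) rather than exactly 30%, average power at 40 enrolled is 75.0% (normal) or 71.9% (t), so the answer hardly moves.

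**Attrition that 40 enrolled can absorb.** To keep 32 evaluable, attrition may not exceed 1 − 32/40 = 20%. That meets 80% by the normal approximation only, since 32 evaluable gives 78.2% by the t interval. By the t interval 80% needs 34 evaluable (80.8%), hence 34/0.70 = 48.6, or 49 enrolled. At 40 enrolled, 34 evaluable would require attrition of no more than 1 − 34/40 = 15%.

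**The case against.** The case for leaving the text alone is reasonable. Section 8.4.2 says how many cases are needed, and 46 lies inside the range of 40 to 50. Nothing tells the sponsor to stop at 40, so the sections can be read together as a target of 46 within an operational window. The objective is exploratory. The shortfall needs both enrolment below 46 and attrition near the 30% allowance. It is also small beside the uncertainty in the inputs: at 28 evaluable, normal-approximation power returns to 80% if the SD is 9.44 rather than 10 (5√28/2.802), or if the true mean is 86.3 rather than 86 (81 + 2.802 × 10/√28). Both inputs are round figures taken from cases with other cone designs.

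Most of this stands, and it settles the weight of the point. It does not remove the point. A range that contains 46 is still satisfied at 40, and the stated 80% does not hold there at the plan's own attrition.

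Two stronger readings are tempting, and the documents support neither. A reader might infer that the exploratory test will be underpowered. The documents do not fix the final count, and at 46 to 50 enrolled the plan's formula gives at least 80%. A reader might also infer that the minimum must be raised to 46. That would align the sections, but it asks for up to 6 more implanted cases for an exploratory aim. It would also give only 78.2% if the interval in Section 8.1.8, whose type is not named, is a t interval.

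**Conclusion.** The inconsistency is real and minor. At the permitted minimum of 40 enrolled and the planned 30% attrition, power on the exploratory KSS test is about 75% by the plan's normal approximation, or 72% by a t interval, against the stated 80%. By the plan's formula the gap exceeds 2 points only at 40 to 42 enrolled and closes at 46.

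These figures assume SD 10, a true mean of 86, one-sided 2.5% and evaluable counts rounded down. The first three are the values that reproduce the plan's own 32. The point concerns agreement between sections on sample size. It does not question the test, the margin or the primary analysis, and the 145 is unaffected.

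**What to change.** Restate the power in Section 8.4.2 for the whole permitted range, for example:

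> Across the permitted 40 to 50 central-cone cases, at 30% attrition (28 to 35 evaluable), power is about 75% to 84% (normal approximation) or 72% to 82% (t interval); 80% by the normal approximation requires 46 enrolled.

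This costs one sentence. Section 2.3 and the Synopsis rows can stay as they are, and no extra cases are needed.

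If the sponsor would rather make 80% hold at the minimum, the lower limit would change in three places: to 46 on the plan's formula, or to 49 if the analysis uses a t interval. Both lie within the existing upper limit of 50. The cost is up to 6 or 9 more central-cone cases than the present minimum, and the documents do not show whether that is feasible. For an exploratory objective, the sentence is the proportionate choice.

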8.4.3 Interim Analyses

No interim analysis is planned.

8.4.4 Analysis Population

Per Protocol Population: The study population for analysis will include all noncensored subjects who receive a Triathlon TS with Triathlon Tritanium Cone Augment and are available for efficacy evaluation at the 2-year primary endpoint. The primary and secondary efficacy analyses will be based on the per protocol population.

Safety Population: The safety population will include all non-censored subjects who received Triathlon TS with Triathlon Tritanium Cone Augment. The safety analysis will be based on the safety population.

9 Study Monitoring, Auditing, and Inspecting

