4.3 Early Withdrawal of Subjects

When and How to Withdraw Subjects

In the event that the subject is discontinued by the investigative center prior to the final study evaluation, the subject will be notified by the center that he/she is no longer in the study and a Study Termination eCRF will be completed.

The following is a list of reasons for which subjects may be withdrawn and the date of termination that should be used on the Study Termination eCRF in each situation. This list is not all inclusive:

Termination Reason	Date of Termination
Death	Date of death
Investigative center termination	Date of study close-out visit
Lost to follow-up	Date Stryker termination approval given
Voluntary withdrawal	Date subject notified center of withdrawal
Revision/removal of study device	Date of revision/removal procedure
Study device not implanted	Date of surgery
Surgery not performed	Date Stryker termination approval given

At the time of study surgery it is required that the following components are implanted to be included in the analysis:

- Triathlon Tritanium Femoral Cone Augment or Central Femoral Cone Augment and/or Tibial Cone Augment
- Triathlon TS Femoral Component
- Triathlon TS Universal Tibial Baseplate
- Triathlon TS Tibial Insert or Triathlon PS Tibial Insert

Revision or removal of the Triathlon Tritanium Cone Augments for aseptic loosening constitutes a failure. Revision or removal of all implanted Triathlon Tritanium Cone Augments for any reason requires study termination for the subject.

If revision of the Tibial Insert or the Patellar Component is required during the study, the event does not constitute a failure or study termination.

Patellar component revision at the time of study surgery is optional. However, if the subject requires patellar component revision a Triathlon Patellar Component must be used. If the patellar component is not revised at the time of study surgery and is later revised, it must be revised to a Triathlon Patellar Component. This event is considered a reoperation and does not constitute a failure or study termination.

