7.6 Protocol Deviations

Any major deviation from this protocol will be recorded in Stryker's Clinical Trial Management System and must be reported to the EC/IRB by the investigational site according to their reporting procedures. Major protocol deviations for this study may include the following; this list may not be all-inclusive:

- Informed consent deviations, including but not limited to:
 - Study procedures performed prior to informed consent
 - o Incorrect informed consent version used
- Patient enrolled does not meet the inclusion/exclusion criteria
- Protocol specified study component(s) not implanted
- Visit deviations, including:
 - o Unavailable primary endpoint

If the center anticipates a possible protocol deviation, the investigator or SC should contact Stryker for guidance.

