8.1.4 Primary Efficacy Hypothesis

The primary hypothesis to be tested will be that the success rate at 2 years postoperative with the Triathlon Tritanium Cone Augments is not worse than 97.2% with a non-inferiority margin of 2.5%. That is, the following hypothesis will be tested:

Ho: Pt <= 97.2% - 2.5% HA: Pt > 97.2% - 2.5%

Here, Pt is the success rate at 2 years postoperative with the Triathlon Tritanium Cone Augments. A case success at 2 years is defined as no incidence of revision/removal of femoral or tibial cone augment for aseptic loosening within 2 years.

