8.1.5 Primary Efficacy Analysis

A 90% two-sided confidence interval will be computed for the success rate at 2 years. If the lower bound of the confidence interval is greater than 94.7%, then the non-inferiority hypothesis will be supported; that is the 2 year success rate is non-inferior to 97.2% with a margin of 2.5%. If the lower bound of the confidence interval is greater than 97.2% then it is supported that the 2 year success rate is superior to 97.2%.

The Kaplan-Meier survival curve of revision/removal of femoral or tibial cone augment will be displayed using SAS/PROC LIFETEST.

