8.3 Missing Data

No missing data will be imputed.

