17.**	Does the subject have any of the following conditions [Does subject have conditions]	[MORBIDYN] [CmpCMORBID] Yes [COMORBID] Myocardial infarction Congestive heart failure Peripheral vascular disease Cerebrovascular disease Cerebrovascular disease Dementia Chronic pulmonary disease Connective tissue disease Peptic ulcer disease Mild liver disease Diabetes without organ damage Diabetes without organ damage Hemiplegia or paraplegia Moderate or severe renal disease Malignant tumor (any) Leukemia Lymphoma Moderate or severe liver disease Metastatic solid tumor HIV
18.**	Concurrent Medical Conditions [Concurrent Medical Conditions]	[CMCYN]

			[cmpIMM] 🖃	
		-	Immunologic / Lymphatic	
			[IMM]	
			A200	
			Musculoskeletal	
			[MUS]	
			A200	
			[cmpNEUR] 🗆	
			Neurologic	
			A200	
			Psychologic	
			[PSYC]	
			A200	
			respiratory	
			A200	
			[cmpSUBD] 📃	
			Substance Dependence	
			[SUBD]	
			A200	
			A200	
			[cmpOTCMC] 🗌	
			Other	
			(Specify)	
			A200	
		No		
C	monto IDM SEI	0		
Lom	ווופות: [ככב_זעט]	DMC		
19. ✔	[Comments]			
		A200		
20.	Charlson-Deyo Comorbidity Index [read-only]	[CCI]		
		N2		
Key	: [✔] = Source verification required [b] = Base Unit []] = Item is col	lapsible		
Not Not	Note: Source verification critical settings made in InForm will override any settings made in Central Designer. Note: Collapsible settings are only available to users who have the rights to edit the item.			

TriathCone: CENSOR (CENSOR) [CENSOR]			
С	CENSOR [CENSOR]		
1.	Censor from Analysis [hidden] [Censor from Analysis]	[CENSORFA] () [cmpCENSOR] Yes [CNSRDT] Date Censored Req ↓ / Req ♥ / Req ♥ (2015-2025) [CNSREASN] Censor Reason A200	
	Key: [*] = Item is required [✓] = Source verification required Note: Source verification critical settings made in InForm will override any settings made in Central Designer.		

Tria	TriathCone: Knee Society Score: Pre-Op (PREKSS2011) [PREKSS2011]			
1.* ✔	Visit Date [Visit Date]	[KSSDOV] Req V / Req V (2015-2025)		
2.* ✓	Charnley Functional Classification [Charnley Functional Classification]	[CHARNLY] A Unilateral Knee Arthritis B1 Unilateral TKA, opposite knee arthritic B2 Bilateral TKA C1 TKR, but remote arthritis affecting ambulation C2 TKR, but medical condition affecting ambulation C3 Unilateral or Bilateral TKA with Unilateral or Bilateral THR		
Obje	ective Knee Indicators [PREKSS_S2]			

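### The primary analysis set can exclude the failures it is meant to count, because a case whose cones are all removed leaves the study and nothing keeps it in the 2-year analysis

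*Combined protocol and SAP*

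**What the plan says.** **Outcome.** Section 8.1.4 defines a case success at 2 years as "no incidence of revision/removal of femoral or tibial cone augment for aseptic loosening within 2 years"; section 8.4.2 repeats this. Section 4.3 agrees: "Revision or removal of the Triathlon Tritanium Cone Augments for aseptic loosening constitutes a failure".

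**Termination.** The same section adds: "Revision or removal of all implanted Triathlon Tritanium Cone Augments for any reason requires study termination for the subject". Its table dates that termination to the revision or removal procedure.

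**Analysis set.** Section 8.4.4 admits to the per protocol population only non-censored subjects who received the device and "are available for efficacy evaluation at the 2-year primary endpoint. The primary and secondary efficacy analyses will be based on the per protocol population". The safety population has no 2-year condition but is also limited to non-censored subjects.

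**Surrounding rules.** Section 7.6 lists "Unavailable primary endpoint" under visit deviations. Section 8.3 reads: "No missing data will be imputed". Censoring is not defined in the text; the CENSOR form in Appendix G holds only a hidden item, "Censor from Analysis [hidden] [Censor from Analysis", with a date and a free-text reason. Section 8.1.5 bases the decision on the lower limit of a 90% interval against 94.7% and names no interval method. On survival it says only: "The Kaplan-Meier survival curve of revision/removal of femoral or tibial cone augment will be displayed using SAS/PROC LIFETEST".

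**The concern.** The outcome definition and the population definition are written separately, and nothing joins them. A single-cone case revised for aseptic loosening at, say, nine months is a failure under 8.1.4 but is terminated at nine months under 4.3. It has no 2-year evaluation, and it may or may not be flagged as censored. Taken word for word, 8.4.4 then removes it from numerator and denominator alike. The same holds for a two-cone case that loses both cones; a two-cone case that loses one is not terminated.

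This affects the study's primary hypothesis test. If the qualifying event also takes the case out, the observed success rate drifts towards 100% whatever the device does, and non-inferiority could be declared at or above the loosening rate the margin is meant to exclude. Two competent programmers could obtain different primary results from this text, and choosing between readings after the failures are known would not be credible.

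**Working it through.** **Inputs from the plan.** Null boundary 97.2% − 2.5% = 94.7% success, so 5.3% failure (8.1.4, 8.1.5). Two-sided 90% interval, i.e. one-sided 5% (8.1.5). Expected success 98.8%, 100 evaluable cases, 80% power, 30% loss, 145 enrolled (8.4.2).

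**Plan's own figure.** The arcsine formula n = [(z₀.₉₅ + z₀.₈₀)/h]², with h = 2·arcsin√0.988 − 2·arcsin√0.947 = 0.245, gives (2.486/0.245)² ≈ 103, against the stated 100. Inflation gives 100/0.7 = 143 against the stated 145. The sample size is close enough and is not in dispute here.

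**Failures tolerated at n = 100.**

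| Failures | Exact lower limit | Wald lower limit |
|---|---|---|
| 0 | 97.05% | – |
| 1 | 95.34% (passes) | 97.36% |
| 2 | 93.84% (misses) | 95.70% (passes) |
| 3 | 92.43% | 94.19% (misses) |

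The rule therefore allows one failure with exact limits and two with Wald limits. At the planned 98.8%, 100 × 0.012 = 1.2 failures are expected, so a single case can decide the result.

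**Single data sets, exact limits.**
- Two failures in 100: 93.84%, misses. Drop one, leaving 1 failure in 99: 95.30%, passes.
- Five failures in 100: 89.8%, misses. Drop all five, leaving 95/95: 96.9%, passes.
- With no failures left, the lower limit is 0.05^(1/n). It is 94.70% (just below the bound) at n = 55 and 94.79% at n = 56, so any set of 56 or more passes.

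**Chance of declaring non-inferiority.** Let q be the true failure rate and d the share of failures dropped. The failure rate among analysed cases is p = q(1 − d)/(1 − qd). At q = 5.3%, p is 5.30%, 4.03%, 2.72%, 1.38% and 0% for d = 0, 25, 50, 75 and 100%. With 100 analysed cases and X ~ Binomial(100, p):

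| Share dropped (assumed) | Exact, P(X ≤ 1), q = 5.3% | Wald, P(X ≤ 2), q = 5.3% | Exact, P(X ≤ 1), q = 8% |
|---|---|---|---|
| 0 | 2.8% | 9.5% | 0.2% |
| 25% | 8.5% | 23% | 1.4% |
| 50% | 24% | 49% | 7.6% |
| 75% | 60% | 84% | 37% |
| 100% | 100% | 100% | 100% |

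Starting instead from 100 cases before any are dropped changes the exact 5.3% column only slightly, to 2.8%, 8.9%, 25%, 62% and 100%.

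**Superiority.** With no failures, the exact limit exceeds 97.2% only from n = 106 (0.05^(1/105) = 97.19%; 0.05^(1/106) = 97.21%), so it is out of reach at n = 100.

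**Check of the repair.** Simulation with 145 implanted cases, 30% exponential loss by 24 months, constant failure hazard (both shapes assumed) and 20,000 runs; for the log-log rule, runs without events use the exact limit:

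| Rule | P(non-inferior), 5.3% failure | P(non-inferior), 1.2% failure |
|---|---|---|
| Kaplan-Meier, log-log limits | 2.9% | about 73% |
| Kaplan-Meier, plain Greenwood limits | 10.3% | 93% |
| Proportion, failures kept, lost event-free cases dropped, exact limits | 1.0% | about 57% |

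The third rule is biased against the device: its mean estimate is 93.7% when the true rate is 94.7%, because failures before loss are counted while event-free cases lost early are not.

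**The case against.** The best reply is that the plan mostly uses the word endpoint for the event, not the visit. The synopsis speaks of an endpoint of revision or removal for aseptic loosening, 8.1.1 names the revision itself as the primary parameter, and 8.1.4 counts incidence within two years. On that view a cone revised at nine months has a fully known outcome, nothing about it is unavailable, and the no-imputation rule does not apply. Section 8.4.2 plans on 98.8% success, which presumes that failures are counted. Appendix G places the CENSOR form at the baseline visit, and 4.3 lists components required for inclusion in the analysis; together these suggest that censoring was meant for eligibility or device reasons. Revision dates and device status are captured on the adverse event and termination forms without a 2-year visit.

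Much of this stands as evidence of intent, and the kinder reading is probably what was meant. It does not supply the missing rule. Section 8.1.4 says what a failure is; 8.4.4 says who is analysed; neither refers to the other. Section 7.6 ties availability of the endpoint to a visit, and a free-text censoring reason constrains nothing. That the data exist is not a rule for using them.

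The objection is also right that the dropped shares are assumed, that 100% is an upper bound because two-cone cases losing one cone stay in, and that the 9.5% starting value in the Wald column comes from the unnamed interval method and not from this gap. The all-cause revision rates in 8.2.2 use the safety set, so the events would still be reported unless flagged as censored, but they do not enter the primary test.

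**Conclusion.** The concern holds, and the plan must be changed. The text permits a reading in which failures leave the primary analysis because they are failures, and no sentence rules it out. With exact limits and 100 analysed cases, the false-positive rate at the null boundary rises from 2.8% to 8.5%, 24% or 60% when a quarter, a half or three quarters of failures are dropped, and to 100% when all are. These figures depend on the assumed share and on the interval method; the documents give neither. The conclusion does not depend on the exact share, since dropping one failure can reverse the decision.

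**What to change.** In 8.4.4 and 8.1.5:

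1. State that any revision or removal of a cone for aseptic loosening within 24 months is a failure and stays in the primary set, whatever the case's termination, censoring or 2-year visit status.
2. Define censoring with prespecified reasons that the endpoint event cannot trigger. This definition is also all the safety population needs.
3. Preferably, estimate the 2-year success rate and its 90% interval by Kaplan-Meier in all implanted cases, with event-free cases that are lost, die or have cones removed for another reason censored at that date. Name the interval, for example log-log limits with the exact binomial limit if there are no events. Report the simple proportion as a sensitivity analysis.

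Items 1 and 2 close the gap. Item 3 avoids the downward bias that arises if failures are kept while event-free losses are dropped. If the sponsor keeps the proportion as primary, Kaplan-Meier should be the sensitivity analysis.

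The cost is a few sentences and no new visits. The planned curve must be restricted to aseptic-loosening events. Cone revision dates are on the adverse event form, but its septic/aseptic loosening items name the femoral, patellar and tibial components and not the cones, so the cause of each cone revision has to be taken from the adverse event record. The reported success rate may be less favourable. Power at 98.8% success is about 73% with Kaplan-Meier log-log limits under the simulated loss, below the planned 80%; the exact binomial rule with 100 analysed cases has only 66%, so the shortfall does not come from Kaplan-Meier itself.
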